## **8.2 Serious adverse events (SAEs)**

- a. Table: Number (%) of subjects with an SAE by MedDRA System Organ Class (SOC) and Preferred Term (PT); number (%) of subjects with any SAE. This table will include all SAEs, irrespective of time from randomization to the date of onset of the SAE (i.e. including any SAEs reported after the day of the Day 28 evaluation). A second table will be generated including only SAEs with onset dates through to the day of the Day 28 visit. In these tables, subjects with SAEs will be counted (e.g. counting a subject with multiple SAEs with the same PT only once for that PT).
- b. Table: Number of SAEs by MedDRA System Organ Class (SOC) and Preferred Term (PT); number (%) of SAEs. This table will include all SAEs, irrespective of time from randomization to the date of onset of the SAE (i.e. including any SAEs reported after the day of the Day 28 visit). A second table will be generated including only SAEs with onset dates through to the day of the Day 28 visit. In these tables, SAEs will be counted (e.g. counting multiple SAEs with the same PT within the same subject).
- c. List of SAEs: Randomized arm, subject ID, site, age, pregnancy status, days from randomization to Day 28 visit, days from randomization to SAE, days from start of first infusion to SAE, SAE (MedDRA SOC and PT, and verbatim description), ICH seriousness criterion met, severity grade, relatedness to study intervention, outcome (sort by randomized arm, subject ID, days from randomization to SAE, MedDRA SOC and PT).

## **8.3 Adverse events (AEs)**

Note: The protocol requires reporting of Grade 3 or higher AEs.

- a. Table: Number (%) of subjects with an AE by MedDRA System Organ Class (SOC) and Preferred Term (PT) and severity grade; number (%) of subjects with any AE. This table will include all AEs through to the Day 28 visit. In this table, subjects with AEs will be counted (e.g. counting a subject with multiple AEs with the same PT only once for that PT).
- b. Table: Number of AEs by MedDRA System Organ Class (SOC) and Preferred Term (PT) and severity grade; number (%) of AEs. This table will include all AEs through to the Day 28 visit. In this table, AEs will be counted (e.g. counting multiple AEs with the same PT within the same subject).
- c. List of AEs: Randomized arm, subject ID, site, age, pregnancy status, days from randomization to Day 28 visit, days from randomization to AE, days from start of first infusion to AE, AE (MedDRA SOC and PT, and verbatim description), severity grade, relatedness to study intervention (sort by randomized arm, subject ID, days from randomization to AE, MedDRA SOC and PT).

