5.9 Study Plasma Administration

Study plasma should be administered as soon as possible. The plasma should be started no later than 12 hours after randomization for units that are available at a site, and no later than 24 hours for units that are shipped from the repository for that subject. The plasma infusion rate will be determined by the individual sites based on institutional policy.

Before administration of study plasma, the investigator (or designated study staff) must verify the plasma label(s) to confirm that the DIN(s) on the plasma unit(s) match the IWRS randomization notification email for the subject, as well as to confirm the appropriate dose to be administered (refer to Section 5.7). Plasma DIN(s) and plasma product code(s) should be recorded in source documents at the time of infusion along with the volume administered.

The calendar date and 24-hour clock time for study plasma administration should be recorded for the start and end of each infusion. The intervals between units may occur per a site's blood establishment SOPs and/or normal practice. Pretreatment to minimize transfusion reactions (e.g. acetaminophen, diphenhydramine, etc.) according to local institutional policies are permitted in this study, but any such medications should be captured as concomitant medications.

If an AE develops during infusion, the infusion may be slowed temporarily or permanently discontinued, as deemed appropriate by the investigator. As a guide, local side effects (e.g., infusion site burning) or non-allergic systemic effects (e.g., chills) can generally be alleviated by slowing the rate of infusion, whereas allergic side effects (e.g., rash, wheezing, hypotension) should result in the cessation of study plasma infusion. All grade 3 or grade 4 AEs, and all SAEs occurring during study plasma administration should be captured as noted in Section 10.2. Additionally, any AEs resulting in plasma discontinuation (regardless of AE grade) should be recorded.

The investigator is ultimately responsible for making the decision to slow or stop study plasma infusion. If the infusion is discontinued, the subject should be treated according to best available local practices and procedures, and the Medical Monitor should be notified. Reason(s) for premature discontinuation of any plasma infusion must be documented in the medical record (source document) and on the eCRF.

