6.3.1.3 Medical History

The investigator (or designee) will take a medical history following consent and conduct a complete physical examination. The following information should be recorded:

- Day of onset of influenza symptoms
- Influenza vaccination in the current season
- History of chronic medical conditions
- Any acute medical problems from the current hospitalization (including laboratory abnormalities)
- Current use of prescription and OTC medications
- History of allergies
- Additional history to be obtained from pregnant women includes last menstrual period, ultrasonic gestational age (if known), and complications during pregnancy.
- For women who are not of childbearing potential, the reason for this (if known) should be documented.

Medical conditions noted at the time of consent should be recorded in the eCRF. Any conditions that develop after consent should be recorded on the AE page of the eCRF.

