6.3.3 Study Day 0: Baseline Evaluation and Randomization

6.3.3.1 Baseline Clinical Data

- Clinical data must be collected just prior to randomization (no more than 4 hours between collection and randomization).
- Vital signs, including SpO₂. These values may be obtained from clinically collected information if they were obtained within 4 hours prior to randomization. Vital signs should be collected in a complete set within 30 minutes of each other.
 - This can be the same set of vital signs as used at screening as long as they were obtained within 4 hours prior to randomization.
- Clinical data:
 - Assessment of clinical status (6-point ordinal scale)
 - Glasgow coma scale
 - Early warning score
 - NEW score for age \geq 18 years
 - PEW score for age $<$ 18 years
 - Organ dysfunction score
 - SOFA score for age \geq 18 years
 - PELOD score for age $<$ 18 years
 - Measures of clinical support:
 - Hospitalization
 - Oxygen requirement
 - Mechanical ventilator requirement
 - ICU requirement
 - ECMO requirement
 - Chest x-ray finding if performed for clinical indication within 24 hours prior to randomization
- Assessment of ARDS using PaO₂ (or SpO₂), FiO₂, and recent chest x-ray data.

- Note: If the above-listed clinical data assessments were performed for screening and collected < 4 hours prior to randomization, they do not need to be repeated for baseline assessment unless the investigator believes there has been a likely change in the score based on clinical assessment.
- Review new medical conditions, concomitant medication, and evaluate for AEs that have occurred after informed consent.

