10.2 Documenting, Recording, and Reporting Adverse Events

All grade 3 or grade 4 AEs, and all SAEs occurring from the time the informed consent is signed through the Day 28 (end of study) visit will be documented, recorded, and reported. Additionally, any AE leading to plasma discontinuation (regardless of grade) will be documented, recorded, and reported.

At each contact with the subject, information regarding AEs will be elicited by appropriate questioning and examinations and will be:

- immediately documented in the subject's medical record/source document,
- recorded on the AE eCase Report Form (AE eCRF), and
- reported as outlined below.

If a diagnosis is clinically evident (or subsequently determined), the diagnosis rather than the individual signs and symptoms or lab abnormalities will be recorded as the AE.

All abnormal laboratory findings will be reviewed on a routine basis by the PI to identify potential safety signals. All worsening laboratory values should be evaluated as potential AEs:

- If an abnormal laboratory finding is captured as a component of a diagnosis AE term that has already been recorded, the individual abnormal laboratory finding is NOT recorded as a separate AE.
- A laboratory abnormality should be reported as an AE if it requires an intervention or is considered clinically significant by the investigator (all Grade 3 or higher are considered clinically significant for this study). Interventions include, but are not limited to, discontinuation of treatment, dose reduction/delay, additional assessments such as repeating the lab test, or concomitant treatment.

An abnormal lab not included on the DAIDS Table for Grading the Severity of Adult and Pediatric Events (V.2.0, Nov, 2014) should be assessed based on the following grading criteria.

- Grade 1 (Mild) [not reportable]
Events causing no or minimal interference with daily activity
- Grade 2 (Moderate) [not reportable]
Events causing greater than minimal interference with daily activity but not requiring medical intervention
- Grade 3 (Severe) [reportable]
Events causing inability to perform daily activity, or suggests organ toxicity, and/or requires medical intervention
- Grade 4 (Potentially Life-Threatening)* [reportable]
Events causing inability to perform basic self-care functions OR medical or operative intervention indicated to prevent permanent impairment, persistent disability, or death
- Grade 5 (Death) [reportable]

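### SAP 8.2 and 8.3 give the by-arm AE and SAE tables no start point, so events between consent and infusion count and modestly dilute the safety comparison

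*SAP*

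**What the plan says.** **Collection.** Protocol 10.2 covers Grade 3 and 4 AEs and "all SAEs occurring from the time the informed consent is signed through the Day 28 (end of study) visit", and adds any AE that leads to plasma discontinuation. Protocol 6.3.1.3 says "Any conditions that develop after consent should be recorded on the AE page of the eCRF". At baseline, before randomization, sites must "evaluate for AEs that have occurred after informed consent" (Protocol 6.3.3.1). For laboratory values, Protocol 10.2 states that "all Grade 3 or higher are considered clinically significant for this study".

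**Timing.** Screening runs from Day -1 to Day 0. Under Protocol 5.9, infusion starts within 12 hours of randomization for units held on site, and "no later than 24 hours for units that are shipped from the repository for that subject".

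**Tables.** SAP 8.3 on AEs: "This table will include all AEs through to the Day 28 visit". SAP 8.2 on the first SAE table: "This table will include all SAEs, irrespective of time from randomization to the date of onset of the SAE". The second SAE table is limited to "including only SAEs with onset dates through to the day of the Day 28 visit", which is an upper limit only. Tables 8.2a and 8.3a count subjects; 8.2b and 8.3b count events. Days from first infusion appear in listings 8.2c and 8.3c and in no table.

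**Population and test.** The safety sections use the mITT population (randomized, infusion started). Protocol 12.3 compares the proportions with any SAE and with any Grade 3 or higher AE by Fisher's exact test. SAP 8.2 and 8.3 specify no p-value.

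**The concern.** The third secondary objective is the safety of high-titer against low-titer plasma, and Protocol 7.4 asks whether the AE rate is higher, lower or no different. An event before the infusion starts says nothing about that question. The mITT rule removes subjects who never started plasma, but not the pre-infusion events of those who did. Neither document defines a treatment-emergent event. The SAP does fix a time origin elsewhere: the Kaplan-Meier mortality analysis in 8.1c starts at randomization.

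A subject with a pre-infusion event is already in the any-event count, whatever happens later. This pulls the two proportions together and makes a real difference, including a harm, somewhat harder to see.

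**Working it through.** The plan states no power or effect size for the safety comparison, so there is no figure of its own to reproduce on this point.

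**1. Dilution formula.** Let p be the probability of an event after the start of infusion, and q the probability of an event between consent and infusion. Take q as equal in both arms (randomized, blinded, before treatment) and independent of later events. Then

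observed proportion = q + (1-q)p, and observed risk difference = (1-q)(p1-p0).

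A subject's earlier event making a later one uncounted is exactly what produces the factor (1-q). It is not a second loss on top.

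**2. Length of the window.** Day -1 and Day 0 span at most about 2 days, and up to 24 hours from randomization to infusion makes about 3. A typical case is 1 to 2 days, against 28 days of follow-up.

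**3. A plausible q for SAEs.** Protocol Table 11 gives 28/98 = 29% of IRC002 subjects with an SAE. Treating this as a 28-day rate with constant hazard (an assumption), the daily hazard is -ln(1-0.29)/28 = 0.01223, and q = 1-exp(-k × 0.01223 × days), where k is a multiplier for a higher early hazard.

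| Days before infusion | q, k = 1 | q, k = 5 |
|---|---|---|
| 1 | 1.2% | 5.9% |
| 2 | 2.4% | 11.5% |
| 3 | 3.6% | 16.8% |

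The k = 5 column is a stress case. The documents give no hazard by day.

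**4. Effect on a difference.** IRC002 had SAEs in 19/52 = 37% on standard care alone and 9/46 = 20% on plasma, a gap of 17 points. This serves only as a yardstick. That trial compared plasma with no plasma and the lower rate was on plasma, so it is not an example of high-titer harm.

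- q = 1.2%: 17 × 0.012 = 0.2 points lost, leaving 16.8.
- q = 3.6%: 17 × 0.036 = 0.6 points lost, leaving 16.4.
- q = 16.8% (stress case): 17 × 0.168 = 2.9 points lost, leaving 14.1.

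**5. Effect on the Fisher test.** Suppose 100 high-titer and 50 low-titer subjects with true post-infusion rates of 37% and 20% (hypothetical), two-sided 0.05. Exact power:

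| q | Observed rates | Difference (points) | Power |
|---|---|---|---|
| 0 | 37.0% v 20.0% | 17.0 | 54% |
| 1% | 37.6% v 20.8% | 16.8 | 53% |
| 2% | 38.3% v 21.6% | 16.7 | 52% |
| 5% | 40.1% v 24.0% | 16.2 | 48% |
| 10% | 43.3% v 28.0% | 15.3 | 42% |

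**6. Grade 3 or higher AEs.** No rate is given. Safety bloods are drawn before randomization and can follow consent (Protocol 6.3.3.2), and any new Grade 3 laboratory value counts. So q may exceed the SAE figures, but the documents do not allow a number.

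**The case against.** **Masking.** A reader might infer that a pre-infusion event hides a later one altogether. It does not: tables 8.2b and 8.3b count repeated events of the same preferred term within a subject. Masking remains only in the subject-level counts, where it is the (1-q) factor already shown.

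**Intent of the SAE wording.** The sentence "This table will include all SAEs, irrespective of time from randomization to the date of onset of the SAE" might be read as a decision to include pre-infusion events. Its own explanatory clause concerns events after the Day 28 evaluation. Pre-infusion events come in because the SAP is silent on a lower limit and the protocol collects from consent.

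**Laboratory values.** A reader might suppose that every abnormal baseline value in a very ill population becomes an AE. Protocol 6.3.1.3 records acute problems of the current admission, laboratory abnormalities included, as history. Protocol 10.2 directs attention to worsening values, and Protocol 6.3.3.2 accepts clinical results from the 12 hours before randomization, which may predate consent. Only new post-consent abnormalities are at issue.

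**Size.** A q such as 30% for SAEs would need a hazard about 10 times the constant one over 3 days (-ln 0.70 / 0.0367 = 9.7), or about 29 times over 1 day. Nothing in the documents supports that.

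**Descriptive purpose.** Protocol 12.3 calls the AE analysis primarily descriptive, and the listings let a reader pick out events from days before the infusion. Both points stand, and they limit the consequence. The Fisher comparisons are still planned, and no table separates the events.

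**Conclusion.** The gap is real and the effect is modest. Followed as written, the plan counts events from before the infusion in the by-arm tables and in the protocol's Fisher tests. The result is dilution toward no difference by the factor (1-q). It does not favor one arm, since blinded randomization makes these events equally likely in both.

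For SAEs, q of about 1% to 4% costs 0.2 to 0.6 points of a 17-point difference and, in the example above, about 1 to 5 points of power. This rests on a constant hazard, on the IRC002 rate carrying over as a 28-day rate, and on independence of earlier and later events. For Grade 3 or higher AEs q may be larger, and its size is unknown. The change is worth making because it is cheap and matches the mITT population, which already requires that infusion has started. The documents do not support a claim that the safety comparison is invalid.

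**What to change.** In SAP 8.2 and 8.3:

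- Base the subject-level tables (8.2a, 8.3a), the event counts (8.2b, 8.3b) and the Fisher comparisons of Protocol 12.3 on events with onset at or after the start of the first infusion. For the comparison, end at the Day 28 visit.
- Include worsening in grade after the start of infusion where the data record it.
- Order events on the infusion day by onset time where recorded, and count untimed same-day events as post-infusion.
- List events from consent to infusion separately, and keep the from-consent counts as a supplementary table so that nothing collected is lost.

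**Cost.** SAP wording and a derived flag. Protocol 5.9 and 6.3.4 already require the date and clock time of each infusion, and the SAP listings already derive days from first infusion.

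**Downside.** The documents do not say that AE onset time or grade history is captured. Much of the pre-infusion window can fall on the infusion day itself, so without onset times some same-day pre-infusion events stay in the main tables and the correction is partial.

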6.3.9 Study Day 14 (± 2)

If the subject is no longer hospitalized, this visit may occur by telephone. In this case, the assessments below should be restricted to the ordinal scale, oxygen requirements, new medical conditions, concomitant medication, and evaluation for AEs. The subject's ability to provide consent should be evaluated. Any subject who was unable to previously provide consent independently should be administered the informed consent according to institutional policies.

6.3.9.1 Clinical Data on Day 14

- Vital signs, including SpO₂. These values may be obtained from clinically collected information if they were obtained within 4 hours of the study assessment. Vital signs should be collected in a complete set within 30 minutes of each other.
- Clinical data
 - Assessment of clinical status (6-point ordinal scale)
 - Measures of clinical support:
 - Hospitalization
 - Oxygen requirement
 - Mechanical ventilator requirement
 - ICU requirement
 - ECMO requirement
 - Assessment of ARDS using PaO₂ (or SpO₂), FiO₂, and recent chest x-ray data.
- Review new medical conditions, concomitant medication, and evaluate for AEs

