7.4.1 Laboratory Evaluations

All laboratory evaluations (except reference endpoint assays) will be performed at the local CLIA, CLIP, or CAP certified clinical laboratory (comparable certifications that are not listed maybe be used after approval by the sponsor). The same laboratory should be used throughout the study for a given subject. Blood samples will be collected at screening if necessary for ABO typing or pregnancy testing, and on Study Days 0, 1, 3, and 7, for evaluation of routine laboratory safety (chemistry, complete blood count with differential). The investigator is to use the “Division of AIDS Table for Grading the Severity of Adult and Pediatric Adverse Events” Version 2.0, November 2014 which can be found in [Appendix A](#).

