12.4.2 Secondary Endpoints

- Ordinal outcome assessed at Days 1, 2, 3, 7, 14, and 28
- Date of hospital admission and discharge
- Date and cause of death (if applicable)
- NEW/PEW score at Day 0, 3, and 7
- Date/time of supplemental oxygen initiation and discontinuation (if applicable)
- Date/time of ICU admission and discharge (if applicable)
- Date/time of mechanical ventilation initiation and discontinuation (if applicable)
- Date/time of meeting ARDS criteria, date of resolution, and severity (if applicable)
- Date/time of ECMO initiation and discontinuation (if applicable)
- SOFA score for age \geq 18 years and PELOD score for age $<$ 18 years on Days 0, 3, and 7
- Disposition (home, rehabilitation, chronic nursing facility) following the initial hospitalization
- Quantitative PCR for influenza in oral swab on Day 0 and 3.
- Grade 3 and 4 adverse events
- SAEs
- Safety laboratory tests will be collected on Days 0, 1, 3, and 7
- CBC with differential white cell count (to include neutrophil and lymphocyte percentages), hemoglobin, hematocrit, and platelets
- Blood chemistries (creatinine, glucose, total protein, ALT/GPT, AST/GOT, total bilirubin)
 - Hemagglutination Inhibition (HAI) titer Days 0, 1, 3, 7
 - Grade 3 and grade 4 adverse events (AEs)
 - Serious adverse events (SAEs)

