#### **8.4 Changes in laboratory test values and vital signs**

The protocol requires the collection of the following at Days 0, 1, 3 and 7:

- CBC: White cell count and differential white cell count (neutrophil and lymphocyte percentages), hemoglobin, hematocrit, and platelets.
- Blood chemistries: creatinine, glucose, total protein, ALT/GPT, AST/GOT, total bilirubin.
- Vital signs, including SaO2.
- PT, INR.

- a. Figure and associated Table: For each test: median, 25th and 75th percentiles at each required measurement time (min, max and sample size also in table).
- b. Figure and associated Table: For each test: median, 25th and 75th percentiles change from Day 0 at each required measurement time (min, max and sample size also in table).

Note –laboratory abnormalities that are clinically significant, or require an intervention, are captured as AEs above.

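### After Day 7, Grade 3+ laboratory AEs are found only through clinically ordered tests, so the Day 28 AE comparison can partly reflect length of stay

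*SAP*

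**What the plan says.** **Laboratory schedule.** Protocol 7.4.1 sets blood draws at screening if needed, "and on Study Days 0, 1, 3, and 7, for evaluation of routine laboratory safety". Protocol 12.4.2 agrees: "Safety laboratory tests will be collected on Days 0, 1, 3, and 7". Sections 6.3.9 and 6.3.10 list no laboratory tests at Day 14 or Day 28. For a discharged subject at Day 14, "If the subject is no longer hospitalized, this visit may occur by telephone", and Day 28 has the same provision. The notes to Protocol Table 5 limit a telephone visit to clinical status, oxygen need, new conditions, medication and AE questions.

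**AE window.** Under Protocol 10.2, Grade 3 and 4 AEs and SAEs "occurring from the time the informed consent is signed through the Day 28 (end of study) visit will be documented, recorded, and reported". On laboratory findings it adds "all Grade 3 or higher are considered clinically significant for this study". It also says that a value already covered by a recorded diagnosis is not entered again.

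**Analysis.** SAP 8.3a and 8.3b tabulate AEs by SOC, PT and grade: "This table will include all AEs through to the Day 28 visit". Neither separates laboratory from clinical AEs or cuts at Day 7. SAP 8.4 summarises values and changes at Days 0, 1, 3 and 7 by quartiles and range. For graded abnormalities it points back to the AE tables: "laboratory abnormalities that are clinically significant, or require an intervention, are captured as AEs above". Protocol 12.3 compares the proportion with a Grade 3 or higher AE by Fisher's exact test. SAP 8.3 lists no p-value.

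**The concern.** Up to Day 7 both arms share one sampling schedule, and the Précis requires the Day 1, 3 and 7 visits to be in person. From Day 8 a laboratory AE can be recorded only if someone orders a test for clinical reasons. A telephone call cannot detect a symptomless Grade 3 value in a subject who was not sampled. Inpatients are likely to be tested more often than discharged subjects, although the documents give no testing frequency for either.

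Hospital status is also what the primary endpoint measures and what the treatment is meant to change. The opportunity to detect a late laboratory AE may therefore differ by arm as a consequence of treatment. An arm discharged earlier could show fewer Grade 3-4 AEs with no difference in laboratory safety, and an arm discharged later could show more. The affected measure, cumulative incidence of Grade 3 and 4 AEs, is a named secondary safety objective.

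**Working it through.** **1. The plan's own figures.** Whitehead's proportional-odds information with N = 135, allocation A = 2 and two-sided 0.05 is V = N·A / [3(A+1)²] × (1 − Σp̄³), and power = Φ(ln OR × √V − 1.96).

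- OR 2.50: V = 10 × (1 − 0.049) ≈ 9.51, so power = Φ(0.916 × 3.084 − 1.96) = 80.7%. The protocol states 80%.
- OR 2.88: 90.3%. The protocol states 90%.

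The high-titer columns of Protocol Table 12 also reproduce from the low-titer column and the odds ratio, so the table can be used for the Day 7 split.

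**2. Day 7 split from Table 12.**

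| | Low-titer | High-titer, OR 2.50 | High-titer, OR 2.88 |
|---|---|---|---|
| Dead | 10% | 4.3% | 3.7% |
| Alive in hospital | 35 + 25 + 10 = 70% | 20.4 + 23.6 + 13.3 = 57.3% | 18.4 + 22.6 + 13.4 = 54.4% |
| Discharged | 5 + 15 = 20% | 7.9 + 30.6 = 38.5% | 8.2 + 33.7 = 41.9% |

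A gap of this kind is realistic. In the IRC002 post-hoc table (Protocol Table 3), 20/42 (48%) of plasma subjects and 31/45 (69%) of standard-care subjects were alive in hospital at Day 7.

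**3. Detection model.** These inputs are assumptions, not document figures:

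- r = true rate of a new Grade 3-4 laboratory abnormality after Day 7 among Day 7 survivors: 10%, 20% or 40%, the same in both arms and the same whether or not the subject is discharged.
- d_in = chance of detection in hospital: 0.9.
- d_out = chance of detection after discharge: 0, 0.2, 0.5 or 0.9.
- Day 7 hospital status stands for the whole of Days 8-28.

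Detected proportion of all treated subjects = r × (in hospital × d_in + discharged × d_out).

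Example at OR 2.50, r = 40%, d_out = 0: low-titer 0.4 × 0.700 × 0.9 = 25.2%; high-titer 0.4 × 0.573 × 0.9 = 20.6%; gap 4.6 points.

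Gap (low minus high), percentage points of all treated subjects, OR 2.50:

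| d_out | r = 10% | r = 20% | r = 40% |
|---|---|---|---|
| 0 | 1.1 | 2.3 | 4.6 |
| 0.2 | 0.8 | 1.6 | 3.1 |
| 0.5 | 0.2 | 0.4 | 0.9 |
| 0.9 (equal detection) | −0.5 | −1.0 | −2.1 |

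The sign reverses in the last row because more low-titer subjects have died by Day 7, which leaves fewer at risk. With Day 7 survivors as denominator that effect drops out: the gap is 0.7 to 6.5 points for d_out from 0.5 down to 0, and 0 when detection is equal. With equal discharge (OR 1) every gap is 0.

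**4. Effect on Fisher's test.** Take 45 v 90 subjects, d_out = 0, r = 20% or 40%, and assume 30% or 50% of each arm already has a Grade 3+ AE by Day 7. Using the survivor-based rates, the gap in any Grade 3+ AE is 1.6 to 4.5 points. Fisher's test then rejects in 4.6-7.1% of trials, against 3.9-4.4% with no gap.

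**The case against.** The strongest reply is that a gap need not be artefact. Discharged subjects are recovering and probably have fewer true abnormalities than subjects in the ICU or on oxygen. This stands. With d_out = 0 the detected gap is 0.4 × 0.9 × (0.700 − 0.573) = 4.6 points whether discharged subjects have unseen abnormalities or none at all. The planned table cannot tell these two cases apart. That limits any claim about size, but it also supports having a comparison on common sampling.

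Other points that stand:

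- The event and detection rates are assumptions, and zero detection after discharge is the extreme. AEs are elicited at every contact, and readmission brings new tests.
- Clinical AEs are sought in everyone to Day 28, and laboratory AEs to Day 7 are on one schedule. A subject already counted by Day 7 adds nothing to the any-AE proportion.
- AE analysis is primarily descriptive. The tables show PTs, so many laboratory terms can be recognised, and listing 8.3c gives the day of each AE, so a Day 7 cut is possible.

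These soften the concern without closing it. SAP 8.4 never gives the proportion reaching Grade 3-4 by arm, and a cut chosen after unblinding is weaker than one specified in advance.

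A reader might infer that the earlier-discharge arm must look safer by design. The documents do not support that, because the bias needs both unequal discharge and lower detection after discharge. A reader might also infer that every Grade 3 value becomes its own AE, which Protocol 10.2 rules out. Nor does 21 of 28 days without scheduled laboratories mean that three quarters of laboratory AEs are affected: it is a share of days, not of events.

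**Conclusion.** The mismatch between the laboratory schedule and the AE window is in the documents, and SAP 8.3 does not handle it. The resulting bias is conditional: it arises only if discharge differs by arm and detection falls after discharge, and it can run in either direction.

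Its size cannot be derived from the documents. If event rates after Day 7 are 10-40%, equal in both arms and regardless of discharge, with detection 0.9 in hospital and 0 to 0.5 after discharge, the apparent gap is roughly 0.2 to 4.6 points of all treated subjects at OR 2.50. The effect on Fisher's rejection rate is small. The issue is therefore how the by-arm Grade 3-4 AE proportion is read, more than a false safety conclusion. It merits a low-cost change before unblinding.

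**What to change.** 1. In SAP 8.3, tabulate laboratory-based AEs separately from clinical AEs.
2. Add a by-arm comparison of the proportion of subjects who worsen from Day 0 to DAIDS Grade 3 or 4 at the scheduled Day 1, 3 and 7 samples. At each day show the number sampled and the number dead or missing.
3. Add a supportive Fisher comparison of Grade 3+ AEs that counts laboratory AEs with onset through the Day 7 visit and clinical AEs through Day 28. This carries the correction into the test planned in Protocol 12.3.
4. Keep the all-AE table to Day 28, with a footnote that laboratory AEs after Day 7 depend on clinical sampling.

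The cost is one or two derived tables from data already collected, using the grading table already in use. Late laboratory events leave the supportive comparison but stay in the all-AE table and listing. Subjects who die before Day 7 or miss that visit are not sampled, which is why the counts in item 2 are needed.
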